12.4.6.2 Medication Error, Overdose and "Off-label Use"

If a medication error (defined as an unintended failure in the treatment process that leads to, or has the potential to lead to, harm to the subject), overdose or "off-label use" (i.e., use outside of what is stated in the protocol) is suspected, refer to [Section 10.3 Major Protocol Deviations]. Any associated (S)AEs are to be reported in the eCRF. If the AE meets the definition of an SAE, the SAE is also to be reported as described in [Section 12.4.5 Reporting Procedures for Serious Adverse Events] together with the details of the medication error, overdose and/or "off-label use."

12.4.6.3 Misuse/Abuse

Definition of misuse: Situations where the IP is/are intentionally and inappropriately used not in accordance with the intended use as defined in the protocol.

Definition of abuse: Persistent or sporadic, intentional excessive use of medicinal products which is accompanied by harmful physical or psychological effects.

If misuse or abuse of the IP is suspected, the investigator must forward the special situation worksheet to the sponsor by fax or email immediately (within 24 hours of awareness). Any associated (S)AEs are to be reported in the eCRF. If the AE meets the definition of an SAE, the SAE is also to be reported as described in [Section 12.4.5 Reporting Procedures for Serious Adverse Events] together with details of the misuse or abuse of the IP.

12.4.6.4 Occupational Exposure

If occupational exposure (e.g., inadvertent exposure to the IP of study site personnel while preparing it for administration to the subject) to the IP occurs, the investigator must forward the special situation worksheet to the sponsor by fax or email immediately (within 24 hours of awareness). Any associated (S)AEs occurring to the individual associated with or resulting from the special situation are to be reported on the special situations worksheet.

12.4.6.5 (Suspicion of) Transmission of Infectious Agent

If transmission of an infectious agent associated with the IP is suspected, the investigator must forward the special situation worksheet to the sponsor by fax or email immediately (within 24 hours of awareness) and any associated (S)AEs are to be reported in the eCRF. If the AE meets the definition of an SAE, the SAE is also to be reported as described in [Section 12.4.5 Reporting Procedures for Serious Adverse Events] together with the details of the suspected transmission of infectious agent.

12.4.6.6 Suspected Drug-drug Interaction

If a drug-drug interaction associated with the IP is suspected, the investigator must forward the special situation worksheet to the sponsor by fax or email immediately (within 24 hours of awareness). Any associated (S)AEs are to be reported in the eCRF. If the AE meets the definition of an SAE, the SAE is also to be reported as described in [Section 12.4.5 Reporting Procedures for Serious Adverse Events] together with details of the suspected drug-drug interaction.

12.5 Liver Safety Monitoring and Assessment

This is a single dose administration and liver safety monitoring will be applied if any AEs occur that prompt safety consideration.

The purpose of this appendix is to provide guidance for the monitoring of drug-induced liver injury during the course of the study. It should be noted that this section does not specify the EOS analyses of liver enzymes. The EOS liver enzymes analyses will be described in the SAP. Any subject enrolled in a study with active drug therapy and reveals an increase of serum aminotransferases (AT) to $> 3 \times$ ULN or bilirubin $> 2 \times$ ULN should undergo detailed testing for liver enzymes (including at least ALP, ALT, AST and TBL). Testing should be repeated within 72 hours of notification of the test results. For studies for which a central laboratory is used, alerts will be generated by the central laboratory regarding moderate and severe liver abnormality to inform the investigator and study team. Subjects should be asked if they have any symptoms suggestive of hepatobiliary dysfunction.

Definition of Liver Abnormalities

Confirmed abnormalities will be characterized as moderate and severe where ULN is as shown below.

Table 10 Moderate and Severe Liver Abnormalities

| | ALT or AST | | TBL |
|-----------------|------------------|------|------------------|
| Moderate | $> 3 \times$ ULN | or | $> 2 \times$ ULN |
| Severe | $> 3 \times$ ULN | and† | $> 2 \times$ ULN |

ALT: alanine aminotransferase; AST: aspartate aminotransferase; TBL: total bilirubin; ULN: upper limit of normal

†Samples taken simultaneously or within maximum 24 hours.

In addition, the subject should be considered to have severe hepatic abnormalities for any of the following:

- ALT or AST $> 8 \times$ ULN
- ALT or AST $> 5 \times$ ULN for more than 2 weeks.
- ALT or AST $> 3 \times$ ULN and† and* TBL $> 2 \times$ ULN or international normalized ratio (INR) > 1.5 (if INR testing is applicable/evaluated)
- ALT or AST $> 3 \times$ ULN with the appearance of fatigue, nausea, vomiting, right upper quadrant pain or tenderness, fever, rash and/or eosinophilia ($> 5\%$)

† Samples taken simultaneously or within a maximum of 24 hours.

The investigator may determine that abnormal liver function results, other than as described above, may qualify as moderate or severe abnormalities and require additional monitoring and follow-up.

Follow-up Procedures

Confirmed moderate and severe abnormalities in hepatic functions should be thoroughly characterized by obtaining appropriate expert consultations, detailed pertinent history,

physical examination and clinical laboratory tests. The study site personnel are to complete the liver abnormality case report form (LA-CRF). Subjects with confirmed abnormal liver function testing should be followed as described below.

Confirmed moderately abnormal liver function tests should be repeated 2 to 3 times weekly, and then weekly or less if abnormalities stabilize or the IP has been discontinued and the subject is asymptomatic.

Severe hepatic liver function abnormalities as defined above, in the absence of another etiology, may be considered an important medical event and may be reported as a SAE. The sponsor should be contacted and informed of all subjects for whom severe hepatic liver function abnormalities possibly attributable to IP are observed.

To further assess abnormal hepatic laboratory findings, the investigator is expected to:

- Obtain a more detailed history of symptoms and prior or concurrent diseases. Symptoms and new-onset diseases are to be recorded as “AEs” within the eCRF. Illnesses and conditions such as hypotensive events, and decompensated cardiac disease that may lead to secondary liver abnormalities should be noted. Nonalcoholic steatohepatitis is seen in obese hyperlipoproteinemic and/or diabetic subjects, and may be associated with fluctuating AT levels. The investigator should ensure that the medical history form captures any illness that predates study enrollment that may be relevant in assessing hepatic function.
- Obtain a history of concomitant drug use (including nonprescription medication, complementary and alternative medications), alcohol use, recreational drug use and special diets. Medications are to be entered in the eCRF. Information on alcohol, other substance use and diet should be entered on the LA-CRF or an appropriate document.
- Obtain a history of exposure to environmental chemical agents.
- Based on the subject’s history, other testing may be appropriate including:
 - Acute viral hepatitis (A, B, C, D, E or other infectious agents)
 - Ultrasound or other imaging to assess biliary tract disease
 - Other clinical laboratory tests, including INR and direct bilirubin
- Consider gastroenterology or hepatology consultations.
- Submit results for any additional testing and possible etiology on the LA-CRF or an appropriate document.

Study Treatment Discontinuation

In the absence of an explanation for increased liver function tests, such as viral hepatitis, preexisting or acute liver disease, or exposure to other agents associated with liver injury, the subject may be discontinued from study treatment. The investigator may determine that it is not in the subject’s best interest to continue study treatment. Discontinuation of study treatment should be considered if:

- ALT or AST $> 8 \times$ ULN
- ALT or AST $> 5 \times$ ULN for more than 2 weeks

- ALT or AST $> 3 \times$ ULN and† TBL $> 2 \times$ ULN or INR > 1.5 (if INR testing is applicable/evaluated)
- ALT or AST $> 3 \times$ ULN with the appearance of fatigue, nausea, vomiting, right upper quadrant pain or tenderness, fever, rash and/or eosinophilia ($> 5\%$)

† Samples taken simultaneously or within a maximum of 24 hours.

In addition, if close monitoring for a subject with moderate or severe hepatic laboratory tests is not possible, study treatment should be discontinued.

Hy's Law definition: Drug-induced jaundice caused by hepatocellular injury, without a significant obstructive component, has a high rate of bad outcomes, from 10% to 50% mortality (or transplant).

The 2 "requirements" for Hy's Law are:

1. Evidence that a drug can cause hepatocellular-type injury, generally shown by an increase in AT elevations $> 3 \times$ ULN ("2 \times ULN elevations are too common in treated and untreated subjects to be discriminating").
2. Cases of increased total bilirubin (at least 2 \times ULN) with concurrent AT elevations at least 3 \times ULN and no evidence of intra- or extra-hepatic bilirubin obstruction (elevated ALP) or Gilbert's syndrome [Temple, 2006].

FDA Guidance for Industry titled, "Drug-induced Liver Injury: Premarketing Clinical Evaluation" issued by the FDA on July 2009:

1. The drug causes hepatocellular injury, generally shown by a higher incidence of 3-fold or greater elevations above the ULN of ALT or AST than the (nonhepatotoxic) control drug or placebo.
2. Among subjects showing such AT elevations, often with ATs much greater than 3 \times ULN, 1 or more also show elevation of serum TBL to $> 2 \times$ ULN, without initial findings of cholestasis (elevated serum ALP).
3. No other reason can be found to explain the combination of increased AT and TBL, such as viral hepatitis A, B, or C; preexisting or acute liver disease; or another drug capable of causing the observed injury.

References

Temple R. Hy's Law: Predicting Serious Hepatotoxicity. *Pharmacoepidemiol Drug Saf.* 2006;15(4):241-3.

The purpose of this appendix is to provide guidance for the monitoring of drug-induced liver injury during the course of the study. It should be noted that this section does not specify the EOS analyses of liver enzymes. The EOS liver enzymes analyses will be described in the SAP. Any subject enrolled in a study with active drug therapy and who reveals an increase of serum aminotransferases (AT) to $> 3 \times$ ULN (to $> 5 \times$ ULN in subjects with liver metastases) or total bilirubin $> 2 \times$ ULN should undergo detailed testing for liver enzymes (including at least ALP,

ALT, AST and TBL). Testing should be repeated within 72 hours of notification of the test results. For studies for which a central laboratory is used, alerts will be generated by the central laboratory regarding moderate and severe liver abnormality to inform the investigator and study team. Subjects should be asked if they have any symptoms suggestive of hepatobiliary dysfunction.

Definition of Liver Abnormalities

Confirmed abnormalities will be characterized as moderate and severe where ULN is as shown below.

Table 11 Moderate and Severe Liver Abnormalities

| | ALT or AST | | TBL |
|-----------------|--|------|-----------|
| Moderate | > 3 × ULN (in subjects without liver metastases), > 5 × ULN (in subjects with liver metastases) | or | > 2 × ULN |
| Severe | > 3 × ULN | and† | > 2 × ULN |

ALT: alanine aminotransferase; AST: aspartate aminotransferase; TBL: total bilirubin; ULN: upper limit of normal

†Samples taken simultaneously or within maximum 24 hours.

In addition, the subject should be considered to have severe hepatic abnormalities for any of the following:

- ALT or AST > 8 × ULN
- ALT or AST > 5 × ULN for more than 2 weeks (in the absence of liver metastases)
- ALT or AST > 3 × ULN and† TBL > 2 × ULN or international normalized ratio (INR) > 1.5 (If INR testing is applicable/evaluated)
- ALT or AST > 3 × ULN with the appearance of fatigue, nausea, vomiting, right upper quadrant pain or tenderness, fever, rash and/or eosinophilia (> 5%)

† Samples taken simultaneously or within a maximum of 24 hours.

The investigator may determine that abnormal liver function results, other than those described above, may qualify as moderate or severe abnormalities and require additional monitoring and follow-up.

Follow-up Procedures

Confirmed moderate and severe abnormalities in hepatic functions should be thoroughly characterized by obtaining appropriate expert consultations, detailed pertinent history, physical examination and clinical laboratory tests. The study site personnel are to complete the liver abnormality case report form (LA-CRF). Subjects with confirmed abnormal liver function testing should be followed as described below.

Confirmed moderately abnormal liver function tests should be repeated 2 to 3 times weekly then weekly or less if abnormalities stabilize or the IP has been discontinued and the subject is asymptomatic.

Severe hepatic liver function abnormalities as defined above, in the absence of another etiology may be considered an important medical event and may be reported as an SAE. The sponsor

should be contacted and informed of all subjects for whom severe hepatic liver function abnormalities possibly attributable to IP are observed.

To further assess abnormal hepatic laboratory findings, the investigator is expected to:

- Obtain a more detailed history of symptoms and prior or concurrent diseases. Symptoms and new-onset diseases are to be recorded as AEs in the eCRF. Illnesses and conditions such as hypotensive events and decompensated cardiac disease that may lead to secondary liver abnormalities should be noted. Nonalcoholic steatohepatitis is seen in obese hyperlipoproteinemic and/or diabetic subjects and may be associated with fluctuating AT levels. The investigator should ensure that the medical history form captures any illness that predates study enrollment that may be relevant in assessing hepatic function.
- Obtain a history of concomitant drug use (including nonprescription medication, complementary and alternative medications), alcohol use, recreational drug use and special diets. Medications, including dose, are to be entered in the eCRF. Information on alcohol, other substance use and diet should be entered on the LA-CRF or an appropriate document.
- Obtain a history of exposure to environmental chemical agents.
- Based on the subject's history, other testing may be appropriate including:
 - Acute viral hepatitis (A, B, C, D, E or other infectious agents)
 - Ultrasound or other imaging to assess biliary tract disease
 - Other clinical laboratory tests including INR, direct bilirubin
- Consider gastroenterology or hepatology consultations.
- Submit results for any additional testing and possible etiology on the LA-CRF or an appropriate document.

Study Treatment Discontinuation

In the absence of an explanation for increased liver function tests, such as viral hepatitis, preexisting or acute liver disease, presence of liver metastases, or exposure to other agents associated with liver injury, the subject may be discontinued from study treatment. The investigator may determine that it is not in the subject's best interest to continue study treatment. Discontinuation of study treatment should be considered if:

- ALT or AST $> 8 \times$ ULN
- ALT or AST $> 5 \times$ ULN for more than 2 weeks (in subjects without liver metastases)
- ALT or AST $> 3 \times$ ULN and† TBL $> 2 \times$ ULN or INR > 1.5 (If INR testing is applicable/evaluated)
- ALT or AST $> 5 \times$ ULN and† (TBL $> 2 \times$ ULN in subjects with liver metastases)
- ALT or AST $> 3 \times$ ULN with the appearance of fatigue, nausea, vomiting, right upper quadrant pain or tenderness, fever, rash and/or eosinophilia ($> 5\%$)

† Samples taken simultaneously or within a maximum of 24 hours.

In addition, if close monitoring for a subject with moderate or severe hepatic laboratory tests is not possible, study treatment should be discontinued.

Hy's Law Definition:

1. Evidence that a drug can cause hepatocellular-type injury, generally shown by a higher rate than control of people with $3 \times$ AT elevations over the ULN ($2 \times$ elevations are too common in treated and untreated subjects to be discriminating).
2. Cases of increased bilirubin (to at least $2 \times$ ULN) in people with concomitant AT elevation to at least $3 \times$ ULN (but it is almost invariably higher) and no evidence of intra-or extra-hepatic bilirubin obstruction (elevated ALP) or Gilbert's syndrome [Temple, 2006].

FDA Guidance for Industry titled “Drug-induced Liver Injury: Premarketing Clinical Evaluation” issued by the FDA on July 2009:

FDA Guidance for Industry:

1. The drug causes hepatocellular injury, generally shown by a higher incidence of 3-fold or greater elevations above the ULN of ALT or AST than the (nonhepatotoxic) control drug or placebo.
2. Among subjects showing such AT elevations, often with AT levels much greater than $3 \times$ ULN, 1 or more also show elevation of serum TBL to $> 2 \times$ ULN, without initial findings of cholestasis (elevated serum ALP).
3. No other reason can be found to explain the combination of increased AT and TBL, such as viral hepatitis A, B or C; preexisting or acute liver disease; or another drug capable of causing the observed injury.

References

Temple R. Hy's Law: Predicting Serious Hepatotoxicity. *Pharmacoepidemiol Drug Saf.* 2006;15(4):241-3.

12.6 List of Excluded Concomitant Medications

These restrictions are required after ASP0598 Otic Solution or placebo administration on Randomization (Day 1), until completion of study procedures at Day 57 (SAD) / Day 85 (single dose expansion or MAD) / Day 113 (multiple dose expansion) or EOS visit.

- Ear drop agents will be used only for the treatment of otitis media with suppurative ear discharge. Only Ciprofloxacin or Ofloxacin ear drops (does not include steroids) are allowed to be used in the ASP0598 Otic Solution or placebo treated ear. Investigators should minimize treatment with ear drops up to a maximum of 10 days and consider alternative treatment (e.g., oral antibiotics).
- Any other topical agents in the ear canal are prohibited to use in the ASP0598 Otic Solution or placebo treated ear.
- Any otologic procedures (e.g., paper patch or surgeries) to the ASP0598 Otic Solution or placebo treated ear are prohibited.

12.7 Laboratory Assessments

Laboratory tests will be performed at screening for eligibility assessment and sent to the local laboratory for analysis.

Table 12 Clinical Laboratory Tests

| Panel/Assessments | Parameters to be Analyzed |
|-------------------|---|
| Hematology | Hematocrit Hemoglobin Platelets Red blood cell count White blood cell count White blood cell count differential |
| Biochemistry | Albumin Alanine aminotransferase Alkaline phosphatase Aspartate aminotransferase Blood urea nitrogen Chloride Creatinine Creatinine kinase Glucose Lactate dehydrogenase Phosphate Potassium Serum HCG for female subjects Sodium Total bilirubin (total and direct) Total protein |
| Urinalysis | Bilirubin Glucose Ketones pH Protein Red blood cells |

12.8 Ear Care and Water Precautions

These restrictions are required after IP administration at Day 1 until completion of the study procedures at Day 57 (SAD), Day 85 (single dose expansion or MAD), Day 113 (multiple dose expansion) or EOS visit.

- Subjects must refrain from showering or bathing for at least 24 hours after IP administration.
 - Showering or bathing are allowed 24 hours after IP administration. When showering or bathing, follow "How to Keep Your Ear Dry" guidelines.
- Any water activities that risk submersion of the ear (e.g., swimming or surfing) are prohibited throughout the entire study period.
- Are not allowed to use any materials (e.g., Q-tips) placed into the ear canal of the treated ear (ear buds or headphones placed at the entrance to the ear canal are considered acceptable). If ear cleaning is desired, then a soft tissue can be used and placed gently at the entrance to the ear canal.
- Should refrain from activities that can increase the middle ear pressure including plane travel (at least 28 days after IP application), positive pressure ventilation (e.g., CPAP or BiPAP) devices, Valsalva maneuvers, excessive high-pressure nose blowing, diving underwater.
- Must refrain from activities that can excessively increase body temperature (e.g., Sauna) for 3 days after IP application.
- Must refrain from activities that stimulate sweating excessively for 3 days after IP application.

How to Keep Your Ear Dry

To keep water out of your ear when showering and bathing, place half of a cotton ball rolled in **1 tablespoon of petroleum jelly** to the ear.

1. The cotton ball should be completely saturated with petroleum jelly.
2. Place this in the bowl part of the outer ear, covering your ear canal. **Do not shove the cotton ball into the ear canal.** Smooth the edges of the cotton ball down to ensure a good seal.
3. Please use a new cotton ball each time and do not submerge your head underwater with this technique.

[figure not shown]

Other options for keeping your ear dry:

Over the counter options include plastic or soft, moldable silicone earplugs.

It is not recommended to use foam earplugs to keep water out of the ear.

12.9 Modified Brighton Grading Scheme

[figure not shown]
| Grade | |
|-------|--|
| 0 | no abnormalities |
| 1 | canal erythema |
| 1b | canal erythema with otorrhea (ear canal fluid discharge) |
| 2 | canal erythema + swelling, TM still visible |
| 2b | canal erythema + swelling, TM still visible with otorrhea |
| 3 | canal erythema + swelling, TM not visible |
| 3b | canal erythema + swelling, TM not visible with otorrhea |
| 4 | canal erythema + swelling, TM not visible + erythema and swelling of the pinna |
| 4b | canal erythema + swelling, TM not visible + erythema and swelling of the pinna with otorrhea |

Lindisfarne ME, Berwick J, Das P. Clinical Review: Acute Otitis Externa. Available from: <https://www.gponline.com>.

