6.6 Dose Modification

SAD and single dose expansion

Not Applicable.

MAD

On Day 15 or Day 29, treatment can be skipped at the Investigator's discretion based on safety reasons that interrupt IP administration (e.g., ear canal skin irritation, mild otorrhea). Subjects should be encouraged to return to the office for evaluation and additional IP administration within the Day 15 or Day 29 visit windows. In the case that the investigator is unable to conduct IP administration for anything other than safety reasons, consultation with the sponsor may be required.

Multiple dose expansion

The statement above for MAD is also applicable to the multiple dose expansion. Additionally, the treatment on Day 15 or Day 29, treatment will be skipped in cases where complete closure is confirmed. If the perforation is detected on Day 29 after treatment was skipped on Day 15, IP administration can be conducted.

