12.4.4 Criteria for Defining the Severity of an Adverse Event

AEs will be classified for severity using the Clinical Data Interchange Standards Consortium Study Data Tabulation Model Controlled (CDISC) Terminology as described in the table below.

Table 9 Criteria for the Severity of an Adverse Event

| Classification | CDISC Definition |
|-----------------------|---|
| Mild | A type of AE that is usually transient and may require only minimal treatment or therapeutic intervention. The event does not generally interfere with usual activities of daily living. |
| Moderate | A type of AE that is usually alleviated with additional specific therapeutic intervention. The event interferes with usual activities of daily living, causing discomfort but poses no significant or permanent risk of harm to the research participant. |
| Severe | A type of AE that interrupts usual activities of daily living, or significantly affects clinical status, or may require intensive therapeutic intervention. |

AE: adverse event; CDISC: Clinical Data Interchange Standards Consortium.

Modified Brighton Grading Scheme will assess local skin reaction at the application site.

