On Day 1, Week 2 (multiple dose only), and Week 4 (multiple dose only), 1 h after the treatment, the following ear canal reactions of treated ear will be collected.

Did the ear experience an abnormal ear sensation

- No

- Yes
 - Burning
 - Stinging
 - Itching
 - Pain
 - Other

After Day 1, data for the following parameters will be collected:

- Gel visible in the treated ear (Yes, No)
- Gel visible in the middle ear (Yes, No)
- TMP of treated ear completely closed (Yes, No, Unknown)
- Ear pain (otalgia) in the treated ear (Yes, No)
- Status of the treated tympanic membrane (Normal, Abnormal, Abnormal: Myringitis, Abnormal: Hematoma, Abnormal: Other, Not visible)
- Status of the middle ear in the treated ear (Normal, Abnormal, Abnormal: Mucosal inflammation with effusion, Abnormal: Mucosal inflammation without effusion, Abnormal: Other, Not visible)

Local skin reaction around the application site will be examined at 60 minutes after the treatment at Day 1 and throughout the observation period. Skin toxicity will be evaluated by Modified Brighton Grading Scheme as shown below.

Grade	Description
0	no abnormalities
1	canal erythema
1b	canal erythema with otorrhea (ear canal fluid discharge)
2	canal erythema + swelling, TM still visible
2b	canal erythema + swelling, TM still visible with otorrhea
3	canal erythema + swelling, TM not visible
3b	canal erythema + swelling, TM not visible with otorrhea
4	canal erythema + swelling, TM not visible + erythema and swelling of the pinna
4b	canal erythema + swelling, TM not visible + erythema and swelling of the pinna with otorrhea

Pharmacokinetics:

- Serum concentration of ASP0598 (dose escalation part only)

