- 3rd dose: post dose on the dosing day by grade, grade 1 or above, grade 3 or above (MAD and multiple dose expansion)
- Days 2 to 18 by grade, grade 1 or above, grade 3 or above
- \geq Days 19 by grade, grade 1 or above, grade 3 or above

When assessing severity, if the event changes in severity (0, 1, 1b, 2, 2b, 3, 3b, 4 and 4b where Grade 4b is the worst grade) during a time interval for a subject, the event with the worst grade will be chosen. If the event is reported multiple times with missing grade(s) and with non-missing grade(s) during an analysis period for a subject, then the subject will be counted for the non-missing worst grade. If the event is reported multiple times with all missing grade(s) for a subject, then the subject will be counted as a missing grade.

Refer to Section [6.9.1](#) for end day of end of study visit definition.

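### The Modified Brighton scheme has no category for otorrhea without canal erythema, and the worst-grade summaries can drop otorrhea that was graded

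*Protocol*

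**What the plan says.** Protocol 12.9 and SAP 5.4 print the same nine grades: 0, 1, 1b, 2, 2b, 3, 3b, 4 and 4b. Grade 0 is "no abnormalities". Grade 1b is "canal erythema with otorrhea (ear canal fluid discharge" and grade 2b is "canal erythema + swelling, TM still visible with otorrhea". Grades 3b and 4b add otorrhea to grades 3 and 4 in the same way.

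On purpose, Protocol 12.4.4 states "Modified Brighton Grading Scheme will assess local skin reaction at the application site", and SAP 5.4 introduces its copy of the table with "Skin toxicity will be evaluated by Modified Brighton Grading Scheme as shown below". Protocol 4.1.1.2 lists the scale among the blinded safety data that the Dose Escalation Committee (DEC) reviews for each cohort.

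Protocol 6.6 allows a Day 15 or Day 29 dose to be skipped for "safety reasons that interrupt IP administration (e.g., ear canal skin irritation, mild otorrhea". It names skin irritation and otorrhea side by side, as two findings.

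SAP 6.5.4 tabulates each interval by individual grade, and also at grade 1 or above and at grade 3 or above. A subject whose grade changes within an interval takes the worst grade in the printed order, with 4b worst. If only some grades in the interval are missing, "then the subject will be counted for the non-missing worst grade". The subject counts as missing only when every grade is missing. SAP 6.1 bases percentages on subjects with non-missing data.

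**The concern.** The scheme sets out to record otorrhea, since four of its nine grades name it. It does so only as an addition to canal erythema. In an ear with a perforated drum, discharge can come from the middle ear and reach a canal that is not inflamed. The protocol foresees discharge in several places: Protocol 2.1 links the condition to suppurative otitis media, Protocol 6.5 permits certain ear drops for otitis media with suppurative discharge, and Protocol 5.3 allows suction for uncomfortable discharge. Protocol 5.2 excludes active otorrhea, or active treatment for it, within 3 months before Screening, so discharge seen after dosing is a change from the state required at entry.

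Two things are at stake. First, two raters may grade the same ear differently, and the analyst cannot tell which convention was used. Second, even otorrhea that was graded may not reach the tables, because the summaries keep one worst grade per interval. The treatment groups are small, so a single ear matters to the displayed percentages.

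**Working it through.** The plan states no figure on this point, so there is none to reproduce. The check compares the grade definitions and the summary rules, then works out how much one ear moves a percentage.

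**1. The nine grades (Protocol 12.9; identical in SAP 5.4)**

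| Grade | Canal erythema required | Otorrhea included |
|---|---|---|
| 0 | no | no |
| 1, 2, 3, 4 | yes | no |
| 1b, 2b, 3b, 4b | yes | yes |

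Four of nine grades include otorrhea, and none of these four lacks erythema. Only grade 0 lacks erythema. The combination of no erythema with otorrhea has no row. Because the SAP prints the same table, this is not a fault of text extraction.

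**2. What a rater can do with such an ear**

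- Grade 0: right for the canal skin, but the label denies any abnormality.
- Grade 1b: records the discharge, but asserts an erythema that is not there.
- Blank: records neither. Under SAP 6.5.4 the blank is ignored if any other grade exists in the interval.

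The readable text does not say which to use.

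**3. Whether other planned items capture it**

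The items that SAP 5.4 lists for collection after Day 1 are gel in the treated ear, gel in the middle ear, closure, ear pain, tympanic membrane status and middle-ear status. None is otorrhea. Middle-ear status includes mucosal inflammation with effusion, which describes the middle ear and not fluid in the canal. The special-interest term lists in SAP Appendices 1 to 3 contain no ear-discharge term.

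**4. The worst-grade rule**

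The order is 0 < 1 < 1b < 2 < 2b < 3 < 3b < 4 < 4b. Take a subject graded 1b at one visit and 2 at a later visit in the same interval. The worst grade is 2, so the subject appears in row 2 and in grade 1 or above, and the otorrhea appears nowhere. The same happens with 2b then 3, or 3b then 4. The rows for grade 1 or above and grade 3 or above cannot show otorrhea at all, since they merge plain and b grades.

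**5. Effect of one ear on the row for grade 1 or above**

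Inputs: 4 active subjects per SAD cohort, 6 per MAD cohort (Protocol Table 6) and 13 per expansion arm (Protocol 9.1). For one ear graded 0 or 1b, the shift is 100/n.

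| Group | n | Shift, 0 versus 1b | Denominator if all the subject's grades in the interval are missing |
|---|---|---|---|
| SAD active | 4 | 100/4 = 25.0 points | 3 |
| MAD active | 6 | 100/6 = 16.7 points | 5 |
| Expansion arm | 13 | 100/13 = 7.7 points | 12 |

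As an illustration, assume a SAD active group in which one other subject has grade 1. The row reads 1/4 = 25% if the discharging ear is graded 0, 2/4 = 50% if graded 1b, and 1/3 = 33.3% if left blank throughout.

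**The case against.** The strongest reply is about the construct. The scale is for skin reaction at the application site. Discharge through a perforation into a normal canal is not a skin reaction, so grade 0 with the discharge reported as an adverse event is defensible. That is fair, and the fix below adopts this reading. But the documents do not state it, and a scale that names otorrhea in four grades invites a different one.

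A reader might infer that such an ear must be scored 0 or left blank, so that every such record is misgraded. The documents do not support this. Nothing in them forces either choice, and 1b is open too. Rater guidance could also sit in the eCRF instructions (Protocol 12.2.3) or in the figure in Protocol 12.9, neither of which is visible here.

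A reader might also take this to be the usual picture in the trial. Exclusions 1j and 1k in Protocol 5.2 select against ears with recent otorrhea or a high Bellucci grade, and no frequency is given.

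Nor is discharge lost to safety review as a whole. Any unfavourable sign is an adverse event (Protocol 12.4.1), treatment-emergent events are tabulated by system organ class and preferred term, otitis is of special interest, and middle-ear status is summarised by visit. The DEC also sees adverse events and membrane images, and no stopping rule in Protocol 4.1.1.3 uses a Brighton threshold. These routes are real but partial. Protocol 12.4.1.1 says that an abnormal safety assessment associated with the underlying disease need not be reported unless more severe than expected, and an investigator could read discharge that way.

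Finally, the by-grade rows in SAP 6.5.4 do show 1b to 4b separately. That holds only where a b grade is the worst in the interval.

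**Conclusion.** The scheme has no category for otorrhea without canal erythema and no visible rule for grading it, so the recorded value depends on the rater. The summaries also drop otorrhea whenever a higher plain grade occurs in the same interval. One affected ear moves the row for grade 1 or above by 25.0, 16.7 or 7.7 points, according to group size. These shifts are per ear and say nothing about how many ears are affected.

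The conclusion rests on the printed grades and the SAP rules, and on there being no rater guidance in material that cannot be seen. It does not extend to saying that the discharge signal is absent from the safety data, or that any escalation decision would have gone differently. This is a minor weakness in the local safety data that is cheap to repair.

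**What to change.** Leave the severity scale unchanged. Add a separate item, otorrhea in the treated ear (Yes/No), to the microscopic ear examination in Protocol 7.2.5 and 12.9 and in SAP 5.4. State beside the table that the Brighton grade then describes the canal skin reaction, so an ear with discharge and a normal canal has an unambiguous entry on both.

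In SAP 6.5.4 add one row per interval, any otorrhea. Derive it from all records in the interval and not from the worst grade: Yes on the new item, or, for records made before the change, any grade 1b, 2b, 3b or 4b.

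Inserting an extra level such as 0b is the obvious alternative, but it would not do the job. It would stay below grade 1 or above, and the worst-grade rule would overwrite it as soon as a plain grade 1 occurred in the same interval.

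The cost is one eCRF field and one table row per interval. Records collected before the change lack the item, and discharge then entered as 0 or left blank cannot be recovered from the grades. The row will therefore tend to undercount for those records and needs a footnote, especially where placebo subjects are pooled across cohorts.
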